2.0 Introduction

Transgender people commonly experience gender dysphoria defined as distress due to discord between their gender identity and birth sex.¹ The number of transgender Veterans (trans Vets) with gender dysphoria increased ~7-fold from 1,406 in 2006 to 9,608 in 2018 in VA.² Compared to non-trans Vets, trans Vets with gender dysphoria have > 2-fold hazard of suicide mortality.³ Gender-affirming treatments (GATs; e.g. surgery, hormones)⁴ are evidence-based treatments to reduce gender dysphoria, improve mental health and quality of life in trans people.⁵⁻⁹ Receipt of hormones and/or surgery reduced suicidal ideation by 62% among trans people¹⁰ with similar findings noted among trans Vets.¹¹ GATs are medically necessary for gender dysphoria.^{4,12-14} However, not much is known about the barriers and facilitators to accessing and receiving GATs in VA and VA Community Care (i.e., care paid for by the VA in the community)¹⁵ among trans Vets who desire GATs.

Barriers to receipt of GATs reported in a single-site VA study included delays in GAT receipt, need to travel for GATs, lack of clinician competency on trans health, discrimination, violence and lack of patient knowledge about VA GAT coverage.¹⁶ Additional barriers suggested by non-VA studies, include low income, housing instability, and cost of GATs.¹⁷⁻²¹ Barriers to GATs thus, reflect social determinants of health (SDOH) barriers (e.g. discrimination)²² and other barriers (e.g. lack of patient knowledge about GAT coverage). In our ongoing IIR 17-238 using VA data, trans Vets with SDOH barriers, including housing instability, financial strain, and violence were 38% less likely to receive hormones than those without SDOH barriers.²³ Trans Vets frequently experience SDOH barriers, with 28% experiencing housing instability, 31% unemployment, and 19.5% violence.²⁴ Thus, targeting SDOH barriers that are especially salient in the lives of trans Vets along with other barriers are promising approaches to improving GAT access and receipt in VA and VA Community Care (CC).

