3.0 Objectives

Specific Aims

Aim 1. Characterize the GATs received by trans Vets in VA and/or CC. We will expand our VA cohort of 9,608 trans Vets² (IIR 17-238) from 2006-18 to the most recent year of data available at the time of funding. We will then add CC data to characterize the GATs received by trans Vets in VA only, CC only, and VA and/or CC. We will also expand our ongoing work on receipt of hormone therapy in VA to examine it in CC as well.

Aim 2. Identify barriers and facilitators associated with receipt of desired GATs in VA and CC. We will survey a national sample of trans Vets with new gender dysphoria diagnoses identified from Aim 1. Among trans Vets who desire GATs, we will determine SDOH barriers, other barriers, and facilitators associated with receipt of desired GATs in VA and/or CC. Among trans Vets who did not desire GATs, we will determine reasons for not wanting GATs to

distinguish between trans Vets who truly do not desire GAT (e.g., due to nonbinary identity) and trans Vets who may desire GATs if certain barriers to GAT access could be addressed.

^{5.0} **Aim 3. Understand trans Vet experiences related to GAT access in VA and CC.** From Aim 2, we will recruit a purposive sample of trans Vets who received all desired GAT(s), some desired GAT(s), and no desired GAT(s). We will also recruit a national sample of LGBTQ+ Veteran Care Coordinators, who are point persons for trans Vets at VA sites.²⁷ Participant interviews will explore experiences and perspectives on GAT access in VA and CC, how SDOH and other barriers influence GAT access and desire, and suggestions for improving GAT access.

Relevance

Informed by study findings and in partnership with our Stakeholder Advisory Group, we will develop patient-centered implementation strategies to improve GAT access. We will deploy these strategies in a follow-up hybrid implementation effectiveness study to mitigate barriers and enhance facilitators to improve GAT access in VA and CC and promote trans health equity. This work addresses HSR&D priorities of health equity/SDOH, access to care, MISSION Act, underserved LGBTQ+ Veterans; and is informed by our ongoing IIR 17-238.

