5.6 Data Analysis

Database aim 1: The data analyst under the supervision of the PI will produce summary statistics (e.g., proportions, means) for gender-affirming receipt in VA and/or CC (VA/CC). We will characterize gender-affirming receipt by: 1) patient characteristics, including demographics (e.g. race), comorbidities (e.g. mental health conditions) commonly reported by trans individuals, utilization of VA care (e.g. primary care), 2) site (e.g. region, rural/urban) and 3) setting (VA/CC). As appropriate, two-sided chi-square test (categorical variables), t-test (continuous variables) or their nonparametric equivalent tests will be used to test for the statistical significance of the associations of these patient and site characteristics with gender-affirming receipt. We will also compare the characteristics of patients receiving gender-affirming treatment through VA vs. CC.

Survey aim 2: Our analytical goal is to identify barriers and facilitators associated with receipt of desired gender-affirming treatments in VA and/or CC. In keeping with this goal, the data analyst under the supervision of the PI, will conduct the following analyses:

Descriptive analyses: We will obtain summary statistics (e.g., proportions, 95% confidence intervals, etc.) of the distribution of each gender-affirming treatment, degree of receipt of desired gender-affirming treatments, barriers, and facilitators of gender-affirming treatment. We will characterize the degree of receipt of desired gender-affirming treatments in VA and/or CC. We will also characterize barriers and facilitators by degree of receipt of desired gender-affirming treatments in VA and/or CC, recognizing that trans Vets who received all desired gender-affirming treatments could encounter barriers in receipt of these gender-affirming treatments and trans Vets who received no desired gender-affirming treatments could encounter facilitators in trying to receive gender-affirming treatments. We will also characterize the degree of receipt of desired gender-affirming treatments, barriers and facilitators by age, race/ethnicity, gender identity (transfeminine, transmasculine, non-binary), and region.

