Primary analyses: We will conduct bivariate analysis to assess the unadjusted relation of barriers and facilitators with the dependent variables, receipt and desire of gender-affirming treatments in VA and CC. As appropriate, two-sided chi-square tests (categorical variables) or their equivalent non-parametric tests will be used to test the significance of any group differences. We will obtain odds ratios (ORs) and 95% confidence intervals (CI) from separate multivariable logistic regression models, to assess associations between barriers and facilitators for the dependent variables. A multinomial logistic regression model will be used to evaluate associations of barriers and facilitators with the ordinal dependent variable: degree of receipt of desired gender-affirming treatments. These models will adjust for covariates, such as age, race/ethnicity and gender identity. Further, depending on the distribution of respondents across sites, we will examine the distributions of the independent and dependent variables as well as the respondents' characteristics across sites. If there is substantial variation across sites and there are adequate number of respondents (at least 5) in each site, we will adjust for clustering of respondents within sites in the analyses. We will combine sites with small sample sizes into a single cluster for the analyses.

Secondary analyses: To assess interrelationships between barriers, we will examine the overlap of barriers by ascertaining the proportion of trans Vets with various combinations of barriers. To examine this overlap, we will create two variables: 1) a categorical variable, indicating combinations of different barriers (e.g., housing instability only, housing instability and employment, housing instability, unemployment and need to travel for gender-affirming treatments, etc.); 2) number of barriers. We will also explore the effects of these variables in models described in the primary analyses.

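### Aim 2 uses one undivided set of barriers for both desire and receipt; some are met mainly by Veterans who sought treatment, seeking is not among the listed measures, and the affected odds ratios could be biased or reversed.

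*Combined protocol and SAP*

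**What the plan says.** Section 5.6 (Survey aim 2, Primary analyses) will "assess the unadjusted relation of barriers and facilitators with the dependent variables, receipt and desire of gender-affirming treatments in VA and CC". It then takes odds ratios from "separate multivariable logistic regression models, to assess associations between barriers and facilitators for the dependent variables". For degree of receipt, "A multinomial logistic regression model will be used to evaluate associations of barriers and facilitators with the ordinal dependent variable". On adjustment: "These models will adjust for covariates, such as age, race/ethnicity and gender identity". Seeking a GAT is not named as a covariate, a restriction or a stratum. The secondary analyses build a count and a combination variable that mix housing and employment with the need to travel for GATs.

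The barriers named in section 2.0 from a single-site VA study are "delays in GAT receipt, need to travel for GATs, lack of clinician competency on trans health, discrimination, violence and lack of patient knowledge" about coverage. The same section adds low income, housing instability and cost from non-VA studies, and financial strain from the team's earlier work. The Aim 2 measures in section 5.5 include receipt, desire, barriers and facilitators, but not whether the Veteran tried to get the treatment.

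Two passages bear on the problem. Section 3.0 limits the receipt question to Veterans who desire GATs, and for the others says "Among trans Vets who did not desire GATs, we will determine reasons for not wanting GATs". The descriptive analyses in 5.6 recognise that full recipients can still meet barriers, and that "trans Vets who received no desired gender-affirming treatments could encounter facilitators in trying to receive gender-affirming treatments".

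**The concern.** An exposure that arises only on the way to treatment is partly a marker of having tried. In a desire model, Veterans who do not want a GAT have little chance of experiencing such a barrier, so the barrier goes with desire even if it has no effect on it. In a receipt model among desirers, a Veteran who never asked has no receipt. If that Veteran is also recorded as having met no barrier, receipt in the unexposed group falls and the barrier looks less harmful than it is, or even helpful. For a facilitator met only while trying, the same coding exaggerates the benefit.

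Aim 2 is meant to show which barriers go with unmet desire and to separate Veterans who truly do not want GATs from those who might if barriers were removed. Its results feed the implementation strategies. An odds ratio in the wrong direction would misdirect that choice, and the planned false discovery rate control deals with chance, not with this bias.

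**Working it through.** The documents give no prevalence, effect size or power figure for Aim 2, so there is no planned figure to reproduce. All inputs below are assumptions, chosen to show direction and range. Throughout, a barrier is reported only by those who sought the GAT, never-seekers are coded as having no barrier, and never-seekers have no receipt.

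**1. Sorting the named barriers** (sections 2.0, 5.5 and 5.6; about 11)

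| Relation to seeking | Barriers |
|---|---|
| Strictly needs it | delays in receipt (1) |
| Mostly met while seeking, but can be anticipated | travel, cost, clinician competency (3) |
| Either | discrimination (1) |
| Does not need it | housing, unemployment, low income, financial strain, violence, lack of knowledge of coverage (6) |

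**2. Desire, barrier with no effect.** Let 70% of desirers have sought a GAT and half of those have met the barrier: 0.70 × 0.50 = 0.35 exposed. Let a share q of non-desirers report it. OR = [0.35/0.65] / [q/(1 − q)].

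| q | 0.02 | 0.05 | 0.10 | 0.20 | 0.35 |
|---|---|---|---|---|---|
| OR | 26.4 | 10.2 | 4.8 | 2.2 | 1.0 |

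**3. Receipt among desirers.** Let a share t have sought, half of them meet the barrier, and receipt among seekers be 50% with it and 70% without. The OR among seekers is (0.50/0.50) / (0.70/0.30) = 0.43. With never-seekers in the unexposed group, receipt there is 0.35t / (0.5t + 1 − t). The exposed odds are 1.

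| t | Receipt, unexposed | Observed OR |
|---|---|---|
| 0.9 | 0.315/0.55 = 0.573 | 0.75 |
| 0.8 | 0.280/0.60 = 0.467 | 1.14 |
| 0.7 | 0.245/0.65 = 0.377 | 1.65 |

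The OR passes 1 where 0.35t = 0.15t + 1 − t, that is, at t = 1/1.2 = 0.83.

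**4. A second model, with a harmful barrier.** An underlying barrier has prevalence 40%. It lowers desire (OR 0.6; 80% desire without it) and lowers receipt among seekers (OR 0.5; 70% receive without it). Desire with the barrier is 2.4/3.4 = 0.706. The barrier's prevalence is then 0.370 in desirers and 0.495 in non-desirers.

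- Desire, with 70% of desirers seeking: exposure in desirers is 0.7 × 0.370 = 0.259. If 5%, 20% or 40% of non-desirers sought, their exposure is 0.025, 0.099 or 0.198, and the observed OR is 13.8, 3.2 or 1.4 against 0.6. It stays above 1 until 0.259/0.495 = 52% of non-desirers have sought.
- Receipt among desirers: the exposed odds are 2.333 × 0.5 = 1.167. The unexposed odds are 0.441s / (0.189s + 1 − s) for a share s seeking. The observed OR is 3.15, 1.63, 1.16, 0.79 and 0.50 at s = 50%, 70%, 80%, 90% and 100%. Direction reverses below s = 84%. Over receipt ORs of 0.3 to 0.8, baseline receipt of 50% to 85% and barrier prevalence of 20% to 40%, that threshold runs from 51% to 98%.
- A barrier reported whether or not care was sought, such as housing instability: desire OR 0.60 and receipt OR 0.50 to 0.68 over the same range of seeking. There is attenuation but no reversal.
- The seeking-dependent barrier analysed among seekers only: 0.50, the assumed value, by construction.

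**5. Facilitators.** With the inputs of step 3 mirrored (receipt 70% with the facilitator, 50% without), the OR among seekers is 2.33. At t = 0.8 the unexposed receipt is 0.20/0.60 = 0.333, and the observed OR is 2.333/0.5 = 4.67.

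**The case against.** A reader might infer that many of the named barriers can be met only by seekers, that exposure in non-desirers is therefore near zero by construction, and that the Aim 2 odds ratios will be wrong in direction. The documents do not support that. Only delays strictly need seeking; about six of the eleven do not need it at all. The list in section 2.0 summarises earlier studies and is not the survey's exposure list. The title speaks of perceived access, and the Benefits paragraph in 5.1 of perceived barriers, which need no seeking. Section 3.0 expects some non-desirers to have barriers in view. Section 5.5 lists domains, not the questionnaire, so a seeking item may exist. Item wording, routing and skip coding are not given. All of this stands, and it limits the finding to a possibility.

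Routing could also produce a different fault. If branching skips barrier items for non-desirers, the complete-data rule in 5.6 leaves none of them in the desire model, which then cannot be fitted. That moves the problem rather than removing it.

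The illustrations depend on their inputs. At equal reporting (35%) the desire OR is 1.0, and at 10% never-sought the receipt OR keeps its direction. The receipt example treats one GAT; for degree of receipt across several GATs, not seeking one does not mean receiving none. This too stands.

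Lastly, the OR among seekers answers a different question from Aim 2, which concerns all desirers. If travel or cost deters seeking, restricting to seekers removes part of the barrier's effect and can introduce selection. That is a good reason to add a seekers analysis rather than substitute it.

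The restriction to desirers in 3.0 does not settle the matter, because never-seekers remain among the desirers. The caution in the descriptive analyses is not carried into the models.

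**Conclusion.** The concern holds for a limited group of items: delays, and to a lesser degree travel, cost and clinician competency, with discrimination depending on its wording. For these, if the items record experienced barriers and never-seekers are coded as having none, the desire odds ratios are pushed upward and the receipt odds ratios towards or past 1. The desire models are the more exposed: in the second model the direction is wrong unless more than about half of non-desirers sought treatment. For receipt, reversal depends on the share of desirers who sought, with a threshold anywhere from 51% to 98% under the assumptions tried. Neither size nor occurrence can be settled from the documents.

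The social-determinant barriers that need no seeking (housing, employment, income, violence) show no reversal, in a model where they do not themselves alter seeking. The point is worth acting on because 5.6 states neither the population of each model nor the coding of barrier items that do not apply, and stating both is cheap.

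**What to change.** In section 5.6:

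1. Classify each barrier and facilitator item in advance as dependent or not dependent on having sought a GAT.
2. In the desire models, use only items that every respondent can have: social-determinant items, knowledge of coverage, and perceived-barrier items asked identically of all.
3. For those who never tried, code experience-dependent items as not applicable: neither 'no barrier' nor missing data to be imputed. Keep these items out of the barrier count and combination variables for those respondents.
4. If the survey can still be amended, add one item per desired GAT asking whether the Veteran asked for it or tried to get it. Report 'desired but never sought' as its own category. Add a receipt analysis among seekers beside the planned analysis among all desirers, and report desire, seeking and receipt as separate stages.

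The cost is revised text in 5.6 and, for step 4, a short branched item and a survey amendment. The seekers analysis has a smaller sample and is open to selection if a barrier deters seeking; both should be stated with its results.

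The documents do not say whether the survey has been fielded. If it has, steps 1 and 2 can still be done, and the report should state the limitation for the receipt odds ratios. Step 3 needs to know who tried, so it is then possible only if existing items or routing show this.

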We anticipate inviting approximately 10,000 trans Vets with a gender dysphoria diagnosis and/or self-reported gender identity as transgender and gender diverse to participate in the national survey and expect up to 1,500 will enroll and complete the survey. Recruitment for the national survey will consist of direct outreach to prospective research participants identified in Aim 1 through a mailed or emailed recruitment letter and Information Statement alerting Veterans about the survey, providing details about the individuals' rights as a research participant and inviting them to participate in the study. The letter will explain that the survey is entirely voluntary and that if they choose not to participate or to end the survey prior to completion, there will be no penalties or loss of VA benefits. The communication will make clear that the survey responses are confidential and that the Veteran's name or any other personally identifying information will not be used in any report of the survey results. The IRB's telephone number will be provided as a means for the potential participant to use to verify that the study constitutes VA research. Additionally, the study project manager's telephone number will be provided for the Veteran to call with questions about the study or if they wish to opt out of the study.

Veterans will be contacted as follows:

Contact	Method	Specifics
---------	--------	-----------

Contact 1	First Letter	All Veterans with a gender dysphoria diagnosis in the past 2 years and/or self-identified gender identity as transgender and gender diverse will be sent a recruitment letter via mail and/or email inviting them to participate in the study and offering the ability to opt-out, complete the survey online (either through mobile device, tablet or desktop), call in to the study project manager's number to complete the survey with the study manager or request that a paper survey is mailed to them.
Contact 2	Second letter	A second letter will be sent via mail and/or email approximately 10 days after the first letter.
Contact 3	Reminder Postcard	Approximately ten to twelve days after the second letter, we will send a reminder postcard and/or letter and/or email reinforcing basic information provided earlier and directing people to the website or to call the study project manager's number to complete the survey.

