Missing data: In a cross-sectional survey, we expect non-response to the entire survey (unit non-response) or to certain questions in the survey (item non-response). We will try to reduce unit non-response by sending two automated email reminders to Veterans to complete the survey. If we have $\geq 10\%$ unit non-response, we will examine the distribution of characteristics between respondents and non-respondents on measures (e.g., age, race/ethnicity, comorbidities, etc.) available in VA data. If necessary, we will create a weight as the inverse of the probability of response from a logistic regression model that predicts response and include these measures as independent variables. These weights will be used in all analyses to reduce bias due to unit non-response. To mitigate item non-response, we will use validated measures, improve the clarity of questions, and use survey branching logic to reduce response burden. Our primary analysis will assume that data are missing completely at random (MCAR) and include only subjects with complete information or computable variables. For items that have $\geq 10\%$ of missing data, we will examine patterns and predictors of missingness and conduct a sensitivity analysis by

imputing the values under the assumptions of missing at random conditional on the observed data. Comparing results from these analyses to that under the MCAR assumption will allow us to assess the amount of bias due to missing data. We will then adjust final models by including predictors of missingness accordingly.

All analyses will be conducted in SAS (SAS, Cary, NC) on complete data. Our tests of significance will be adjusted for multiple testing using the Benjamini-Hochberg procedure to control for the False Discovery Rate.

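### If response weights are used in the survey analyses, the plan names no variance method that accounts for them, so p-values may be too small and confidence intervals too narrow

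*Combined protocol and SAP*

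**What the plan says.** Section 5.6, Survey aim 2, Missing data, sets out the weighting in three steps.

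- A check: "If we have $\geq 10\%$ unit non-response, we will examine the distribution of characteristics between respondents and non-respondents".
- A conditional weight: "If necessary, we will create a weight as the inverse of the probability of response from a logistic regression model that predicts response".
- Its scope once it exists: "These weights will be used in all analyses to reduce bias due to unit non-response".

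Section 5.2 gives the scale: "We anticipate inviting approximately 10,000 trans Vets with a gender dysphoria diagnosis" (the sentence also covers self-reported identity), and the team "expect up to 1,500 will enroll and complete the survey".

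The methods that would receive the weights are under Primary analyses in section 5.6. For bivariate work, the plan names "two-sided chi-square tests (categorical variables") or non-parametric equivalents, to be chosen as appropriate. For adjusted work, the plan names multivariable logistic models with odds ratios and 95% confidence intervals, and a multinomial logistic model for degree of receipt. SAS is the software, with no procedure named, and p-values are adjusted by Benjamini-Hochberg. The only provision that bears on variance is an adjustment for clustering within sites. It depends on site variation and on at least 5 respondents per site, and its method is not stated.

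**The concern.** A weighted estimate needs a variance that reflects the weights. Unequal weights add variance that the usual chi-square and maximum-likelihood standard errors do not see. If the weights are left on their natural scale and read as counts, the analysis also behaves as if all the invitees had answered. The plan prescribes the weights but not the variance. Its survey tests are described in much the same terms as the chi-square tests for the Aim 1 administrative data, where no response weights arise.

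What is at stake is the main product of Aim 2: the list of barriers and facilitators declared to be associated with receipt of desired treatment. Benjamini-Hochberg takes p-values as given. If they are systematically too small, the false discovery rate is no longer held at its intended level. The list then feeds the strategies to be developed for improving access.

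**Working it through.** The documents give no power calculation, design effect, significance level or weight spread, so there is no figure of the plan's own to reproduce.

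**Inputs from the protocol.** About 10,000 invited and up to 1,500 completers (section 5.2); 10% non-response threshold (section 5.6, Missing data); barrier prevalence 28%, the housing-instability figure (section 2.0), used only in the simulation.

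**Assumptions.** Two-sided 5% tests; coefficient of variation (CV) of the weights from 0.25 to 1.0.

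**Step 1: is weighting likely?** Response is at most 1,500 / 10,000 = 15%, so non-response is at least 85%, against a threshold of 10%. The comparison of respondents with non-respondents will therefore be made. The mean inverse-probability weight would be about 10,000 / 1,500 = 6.67, and higher if fewer respond.

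**Step 2: weights rescaled to mean 1, ordinary variance.** The Kish design effect is deff = 1 + CV². The actual type I error is 2[1 − Φ(1.96/√deff)], the true standard error is √deff times the reported one, and effective n is 1,500/deff.

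| CV | deff | Effective n | True SE / reported SE | Type I error | Coverage of 95% CI |
|---|---|---|---|---|---|
| 0.25 | 1.06 | 1,412 | 1.03 | 5.7% | 94.3% |
| 0.50 | 1.25 | 1,200 | 1.12 | 8.0% | 92.0% |
| 0.75 | 1.56 | 960 | 1.25 | 11.7% | 88.3% |
| 1.00 | 2.00 | 750 | 1.41 | 16.6% | 83.4% |

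**Step 3: unscaled weights treated as counts.** The design effect is multiplied by 6.67. Even with equal weights the standard error is understated by √6.67 = 2.58, and the type I error is 2[1 − Φ(1.96/2.58)] = 45%. For CV 0.25 to 1.0 it is 46% to 59%.

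**Step 4: simulation check.** There were 1,500 null data sets per scenario, each with 10,000 invited, 15% responding and weights estimated by logistic regression. The outcome was either independent of the response predictor (50% prevalence) or dependent on it.

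| Weight CV (approx.) | Ordinary chi-square, rescaled weights |
|---|---|
| 0.02 | 4.5% to 4.7% |
| 0.22 | 5.3% to 5.4% |
| 0.45 | 7.5% to 7.9% |
| 0.71 | 10.4% to 11.1% |
| 1.03 | 16.3% to 16.4% |

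With unscaled weights the rejection rate was 43% to 61%. With a robust (sandwich) variance it was 4.5% to 6.3% over all scenarios, so the remedy restores the level closely. The simulation error of a true 5% rate is √(0.05 × 0.95 / 1,500), or about 0.6 percentage points.

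The simulation covers a single two-by-two association. The logistic and multinomial models and the Benjamini-Hochberg step were not simulated; that they share the problem follows from the mechanism.

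**The case against.** The strongest reply is that the plan is silent on variance rather than wrong about it. A Rao-Scott test is a chi-square test, a survey logistic procedure fits logistic regression, and the plan qualifies its choice of tests as a matter of appropriateness. A competent analyst could follow the text and do everything correctly. This stands as far as it goes. A reader might infer that the plan commits to ordinary formulas and that its p-values will be too small; the documents do not say so, and the claim has to remain conditional. The reply does not close the gap, however. The only alternative offered to chi-square is a non-parametric test, not a weighted one, and the plan leaves open a choice that can change the error rate materially.

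A reader might also infer that the 10% threshold makes weighting certain. It does not: crossing it triggers a comparison, and weights follow only if judged necessary. If respondents resemble non-respondents there may be no weights and no problem. Against that, weights are most likely to be judged necessary when the two groups differ, which is also when the weights vary and ordinary formulas fail.

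Finally, the 45% figure needs unscaled weights to be read as counts. Nothing in the documents says this will happen, so it is a worst case and not the expected size of the error.

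**Conclusion.** The point holds in conditional form. If response weights are created, the plan applies them everywhere and names no variance method that accounts for them. Ordinary formulas would then give p-values that are too small and intervals that are too narrow, and the Benjamini-Hochberg step would inherit this.

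For rescaled weights, a nominal 5% test would reject about 6% to 17% of the time over an assumed weight CV of 0.25 to 1.0, with interval coverage of about 94% down to 83%. The error is negligible if the weights barely vary and are rescaled. These figures rest on the assumed CV and a 5% level, neither of which the documents give. The 15% response is a ceiling, since the protocol expects up to 1,500 completers.

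Whether the 10% threshold and the judgement of necessity should be kept is a separate question about when to weight. This point does not require either to be dropped.

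**What to change.** In section 5.6, under Primary analyses and Missing data, state that whenever response weights are applied:

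- bivariate tests use a Rao-Scott chi-square (for example PROC SURVEYFREQ);
- logistic and multinomial models use design-based or sandwich variance (for example PROC SURVEYLOGISTIC);
- site is the cluster in the same variance calculation when the clustering adjustment applies;
- unweighted results are reported alongside the weighted ones.

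Design-based and sandwich variances do not depend on the scale of the weights, so this wording also removes the count-weight worst case. The cost is a few sentences in the plan, a change of SAS procedure and somewhat wider intervals (by factors of about 1.03 to 1.41 over the assumed CV range, relative to ordinary variance with rescaled weights). No new data are needed.
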